7.6 Risk-to-benefit rationale

The decision to embark upon a clinical study of a medical device requires that the residual risk(s), as identified in the risk analysis, as well as risk(s) to the subject associated with the clinical procedure required by the study plan, be balanced against the anticipated benefits to the subjects.

The Nanostim device conforms to all applicable parts of vertical and horizontal standards that apply to cardiac pacemakers. In addition, Nanostim has considered differences between the LCP with no leads, compared to the standards that specify a pacing lead, and has addressed additional safety characteristics needed to reduce all risks to acceptable levels. Certain performance characteristics cannot be adequately measured pre-clinically and were validated in the pre-market clinical investigation. The present observational study will provide additional validation.

This observational study plan also excludes vulnerable populations (Refer to §18).

The effectiveness of cardiac pacing is well known and accepted.^{5,6} The Nanostim LCP is comparable to existing VVIR therapy and the intended population for the LCP is essentially the same for approved VVIR devices. Clinical evidence already obtained addresses proof of concept of therapy and supports a positive risk-benefit balance.

Implantation of the LCP for cardiac pacing may offer certain advantages as compared to conventional pacemakers. The clinical benefits for this procedure outweigh the risks and thus provide justification for proceeding with this observational study.

8 OBJECTIVES OF THE OBSERVATIONAL STUDY

This clinical study will confirm the clinical performance and safety of the Nanostim LCP system for subjects who are indicated for a VVI(R) pacemaker by following 1000 patients for 5 years. The primary PMCF requirement for this study will be the complication-free rate at 180 days for 300 patients. Complications are defined as serious adverse device effects (SADE).

Sponsor will record and report pacing, sensing, and other performance endpoints listed in §9.1.2. Sponsor will also assess residual risks identified in the risk analysis section, and incidence of anticipated adverse events and adverse device effects listed in Table , §16.8.

9 DESIGN OF THE POST-MARKET OBSERVATIONAL STUDY

9.1 Study design

This is a prospective, non-randomized, single-arm, multicenter, post-market observational study of safety and performance.

9.1.1 Measures to be taken to minimize or avoid bias

- Each institution in this multicenter study will be using the same protocol to ensure consistent data measurement techniques among all Investigators.
- Sponsor will obtain signed Financial Disclosure statements from each participating investigator and Investigator Agreements from each participating site.
- Study endpoints are based on objective measures.

9.1.2 Primary, secondary, supplementary endpoints and additional data

- Primary Safety Endpoint: Freedom from complications (serious adverse device effect) at 180 days. Safety will be measured by reporting the complication rate, defined as SADE (§16.4).
- Supplementary Endpoints: Freedom from complications (serious adverse device effect) at 90 days and 5 years.
- Additional Data:
 - Right ventricular pacing and sensing functions (pacing threshold, R-wave amplitude, battery voltage and pacing impedance performance) at each of the study visits
 - All adverse events
 - Implant success rate,
 - Defined as the number of subjects leaving the implant procedure with an implanted and functioning LCP device, divided by the number of subjects in whom implantation is attempted.
 - Procedure time,
 - Defined as the time from delivery catheter and LCP insertion to removal of the delivery system.
 - Time to discharge,
 - Defined as the time from introducer sheath removal to discharge.

9.1.3 Equipment to be used for assessing the clinical study variables and arrangements for monitoring maintenance and calibration

Device performance is primarily measured with a Nanostim programmer and the implanted Nanostim LCP. The Nanostim programmer does not require scheduled maintenance or calibration.

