Schedule of Assessments	
a. For subjects with de novo Nanostim LCP implant or already implanted with a Nanostim LCP within 3 months of the study start at one of the selected sites
 
Enrollment Assessments
 
 • Inclusion/exclusion criteria • Informed consent • Medical history 
Implant Assessments
 
 • Femoral vein assessment and access • LCP implant • LCP assessment and programming • Assess for adverse events and device deficiencies 
Pre-Discharge Visit
 
 • LCP assessment and programming • Assess for adverse events and device deficiencies 
90-day Visit
 
 • LCP assessment and programming • Assess for adverse events and device deficiencies 
6-month Visit
 
 • LCP assessment and programming • Assess for adverse events and device deficiencies 
Every 6-month follow-up visits thereafter (until the last enrolled subject has completed a 5-year follow-up visit)
 
 • LCP assessment and programming • Assess for adverse events and device deficiencies 
Optional and only for subjects with de novo Nanostim LCP implant or already implanted with a Nanostim LCP within 3 months of the study start at one of the selected sites : 24-hour Holter Recording (involving approximately 25 subjects in the study, any time after first 30 days of follow-up)
 
b. For subjects who participated in the pre-CE mark LEADLESS study
 
Enrollment Assessments
 
 • Inclusion/exclusion criteria • Informed consent • Medical history • Assess for adverse events and device deficiencies 
90-day Visit (if visit occurred within 60-120 days post-implant)

- LCP assessment and programming
- Assess for adverse events and device deficiencies

6-month Visit (if visit occurred within 5-7 months post-implant)

- LCP assessment and programming
- Assess for adverse events and device deficiencies

Every 6-month follow-up visits thereafter (until the last enrolled subject has completed a 5-year follow-up visit)

- LCP assessment and programming
- Assess for adverse events and device deficiencies

The LEADLESS Observational Study

Table 1: Study flow and CRFs

CRFs	Pre-procedure	Procedure	Post-procedure Assessments			Additional Assessments	

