6 JUSTIFICATION FOR THE STUDY DESIGN

This is a study of a CE-marked product within its approved indications, in accordance with its instructions for use. Before this study begins, the manufacturer will have demonstrated conformance of the device with essential requirements, and a positive benefit/risk balance, through pre-clinical testing and clinical evaluation, including a proper pre-market clinical investigation. However, [REDACTED]

[REDACTED] important information about potential residual risks can be gathered in this post-market observational study:

[figure not shown]
- This study may detect rare complications that only become apparent after wider-spread use of the device, again because of the increased sample size and number of physicians implanting the system in this post-market study.
- This study may provide stability data on long-term performance of the study device, through 5 years follow-up.

Consequently, the Sponsor has designed a prospective, non-randomized, single-arm, multicenter, post-market, observational study. This study will follow 1000 patients and will be completed when the last patient reaches the 5 year follow-up visit. The design will include a study population who are at least 18 years of age and who are indicated for a VVIR pacemaker.

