9.3.4 Recruitment and enrollment

Candidates for this clinical study include subjects indicated for a VVI(R) pacemaker. Pre-enrollment records will include evidence of diagnosis indicating need for VVI(R) pacemaker. Preoperative screening to confirm the diagnosis is not considered part of the clinical study; however, the informed consent form will inform the subject that their medical history records used to confirm diagnosis will be incorporated into the study record.

Enrollment begins when the subject provides written informed consent and agrees to participate in the clinical study. A total of 300 subjects are needed to meet the 6-month follow-up sample size. Additional subjects will be enrolled until approximately total 1000 subjects are enrolled and everyone will be followed for at least up to 5 years post implant to document the long term performance of the system.

Patients who participated in the pre-CE mark LEADLESS study, the Nanostim Delivery Catheter pre-CE mark study or were implanted with a Nanostim Leadless Cardiac Pacemaker within 3 months of the study start at one of the selected sites involving physician trainers and study leaders can be enrolled.

For the pre-CE mark LEADLESS study subjects, the data collection will start after consent is obtained and will include any study related adverse event documentation after the subject exited the pre-CE mark LEADLESS study.

For the Nanostim Delivery Catheter pre-CE mark subjects, the data collection will start after consent is obtained.

For subjects who were implanted with a Nanostim Leadless Cardiac Pacemaker within 3 months of the study start at one of the selected sites involving physician trainers and study leaders, the data collection will start after consent is obtained and will include implantation procedure, pre-discharge visit and any study related events (Adverse Event, Device Deficiency, additional visit, etc.).

Additionally, 24-hour Holter data will be collected in approximately 25 subjects any time after the first 30 days of follow-up.

Sponsor anticipates that the clinical study will be completed within 6 years.

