9.4.1 Enrollment assessment

The Investigator will not start any study-specific procedures or alterations of subject care until the informed consent process has been completed and Investigator obtains a signed Informed Consent Form. To determine eligibility, some screening procedures may be necessary. If any of these tests do not fall within the Investigator's standard clinical practice, they will be required for subjects to be enrolled in the clinical study.

During this visit, investigation team will collect medical history data.

In addition:

- For subjects who were previously implanted with a Nanostim LCP at one of the selected sites involving physician trainers and study leaders, investigation team will collect implant procedure data, pre-discharge data and any study related events (Adverse Event, Device Deficiency, additional visit, etc.).
- For pre-CE mark LEADLESS study subjects, investigation team will collect any study related adverse events.

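### The implant success rate in section 9.1.2 has no cohort restriction, so subjects who join only because they already carry the device can be counted and bias it upward

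*Combined protocol and SAP*

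**What the plan says.** Section 9.1.2 lists the implant success rate under additional data. The wording gives the numerator first ("Defined as the number of subjects leaving the implant procedure with an implanted and functioning LCP device"); that count is then to be "divided by the number of subjects in whom implantation is attempted". Neither count is limited to a cohort or to subjects who consented before the procedure.

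Section 9.3.4 opens the study to people who "were implanted with a Nanostim Leadless Cardiac Pacemaker within 3 months of the study start at one of the selected sites involving physician trainers"; the same clause also names the leaders of the study. For this group, "the data collection will start after consent is obtained and will include implantation procedure, pre-discharge visit and any study related events". Section 9.4.1 repeats the instruction for the enrollment assessment: "investigation team will collect implant procedure data, pre-discharge data and any study related events". The schedule of assessments in the synopsis puts subjects "already implanted with a Nanostim LCP within 3 months of the study start at one of the selected sites" in group (a) with the de novo implants, and that group's schedule includes the implant assessments.

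Three other places bear on the point:

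- Section 9.1.4 describes a successful implant in terms of an enrolled subject, and the synopsis and 9.3.4 date enrollment from written consent.
- Section 9.4.3 follows failed attempts for 30 days, but only in enrolled subjects. Section 10.2 adds no entry route for attempts that failed before consent.
- The summary table in 10.1 gives the implant success rate descriptive statistics only, and the text below it specifies a two-sided 90% confidence interval.

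**The concern.** Entry to the already-implanted cohort depends on the outcome being measured. A patient implanted at one of the selected sites shortly before joining can consent and bring a success into the rate. A patient at the same site in the same weeks whose attempt failed cannot join, so that failure is never counted. The cohort can add a failure only if someone was implanted and still left the procedure with a device that did not function.

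Readers will take the rate as the proportion of attempts that succeed. If the cohort is pooled in, the rate sits above that proportion. The confidence interval reflects sampling error only and would not reveal the shift.

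**Working it through.** The documents state no target, expected value or sample size for this rate, so there is no figure of the plan's own to reproduce. The check is who can enter, then how far the rate can move.

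**Who can enter and be counted**

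| Patient | Can enroll? | Implant data collected? | Counted under 9.1.2 as written? |
|---|---|---|---|
| Consents first, attempt succeeds | Yes | Yes | Yes, as a success |
| Consents first, attempt fails | Yes | Yes | Yes, as a failure |
| Implanted at a selected site, consents later | Yes (9.3.4) | Yes (9.3.4, 9.4.1) | Not excluded; a success in nearly every case |
| Attempt failed at a selected site before consent | No route | No | No |

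The third row has no matching row of failures.

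**Formula**

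Let w be the already-implanted cohort's share of counted attempts, p the success rate in prospective attempts, and take the cohort's success as 100%.

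- Pooled rate = (1−w)p + w
- Bias = pooled rate − p = w(1−p)

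Neither w nor p is in the documents; the values below are assumptions. The interval half-width is 1.645 × √(q(1−q)/N), where q is the pooled rate and N = 1000 attempts is assumed from the planned enrollment.

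**Results at p = 96%**

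| w | Pooled rate | Bias (points) | 90% half-width (points) |
|---|---|---|---|
| 5% | 0.95 × 0.96 + 0.05 = 96.2% | 0.2 | 0.99 |
| 10% | 0.90 × 0.96 + 0.10 = 96.4% | 0.4 | 0.97 |
| 20% | 0.80 × 0.96 + 0.20 = 96.8% | 0.8 | 0.92 |

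**Wider range**

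- Smallest corner, p = 98% and w = 2%: 0.02 × 0.02 = 0.04 points.
- Largest corner, p = 90% and w = 30%: 0.30 × 0.10 = 3.0 points.
- The bias equals the half-width, here evaluated at p, when w = 1.645 × √(p(1−p)/1000) / (1−p). That is about 16% for p = 90%, 23% for p = 95% and 36% for p = 98%.

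**Sensitivity to the 100% assumption**

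One cohort subject who left with a non-functioning device would lower the pooled rate by 1/1000 = 0.1 point.

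**The case against.** The best counter-argument is that the plan never says the cohort is counted. No analysis set is given for this rate. Section 9.1.4 speaks of an enrolled subject leaving the procedure, and enrollment begins at consent, so someone implanted before consent was not enrolled on leaving. That reading is possible. But the definition sits in a passage on who is left out of the primary endpoint, and 9.1.2 does not adopt it. The data collection rules and the shared schedule point the other way. What stands is that inclusion follows from the unrestricted wording and is not an explicit instruction.

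The size objection also stands in part. The cohort comes from a short window at selected sites, in a study of up to 100 sites and 1000 patients. A 20% share would mean about 200 such patients, and nothing in the documents points to that many. In all three scenarios at p = 96% the shift is smaller than the half-width. It is still one-directional and avoidable.

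A reader might also infer four stronger things that the documents do not support:

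- **That a share w of all failures is hidden.** The reported failure rate is lower than the prospective one by the fraction w. Counting hidden failures would need the unseen failure rate at the selected sites to equal that elsewhere, and the documents give no rate for either.
- **That the bias defeats the study's rationale.** The visible bullet in section 6 ("again because of the increased sample size and number of physicians implanting the system in this post-market study") concerns detection of rare complications and says nothing about implant success.
- **That the PMCF report would be misleading.** Its requirement is the 180-day complication-free rate (6.1 and 8), and 6.3 promises safety data at that point. No section places implant success in it.
- **That procedure time and time to discharge are distorted by experienced operators.** The site restriction is explicit, but an effect on these times is conjecture. A filter on consent timing would not remove it, since nothing bars those sites from enrolling prospectively.

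**Conclusion.** The point holds in a limited form. As written, 9.1.2 lets subjects selected for a completed implant enter the success rate, while failed attempts at the same sites before consent cannot. If they are counted, the rate is biased upward by w(1−p).

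The size cannot be derived from the documents. Under the assumed p = 96% and shares of 5% to 20%, the inflation is 0.2 to 0.8 points; with a share of 10% or less and p of at least 90%, it is at most 1 point. These figures take the cohort's success as 100%.

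The measure is descriptive, with no visible hypothesis or performance goal. The primary endpoint is not affected by this route. It would go too far to say that the plan orders the pooling or that a reported rate is materially wrong. The change is worth making because the bias is systematic and a single rule removes it.

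**What to change.** In section 9.1.2, state that the implant success rate is computed only in subjects who gave consent for this study before the implant attempt. Naming consent for this study matters: it also keeps subjects from the two pre-CE mark studies out of the denominator. Sections 9.3.4 and 9.4.1 do not ask for their implant procedure data, but nothing expressly excludes them.

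List implant success, procedure time and time to discharge for the already-implanted cohort separately, labelled as coming from subjects who enrolled after implantation.

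The cost is a short addition to the text and a filter in the tables. The rate will rest on slightly fewer subjects and will probably be reported slightly lower. No new data collection is needed.

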9.1.4 Procedures for the replacement of subjects

- If a subject is not successfully implanted with an LCP, signs a consent but does not undergo an implant attempt, Sponsor will account for them in the final report, but will exclude them from the calculation of the primary endpoint (complication-free rate).
 - A successful implant is defined as an enrolled subject leaving the implant procedure with a functioning LCP capable of pacing and sensing.

- The sample size accounts for dropouts; therefore, neither Sponsor nor Investigator will take additional measures to replace subjects.
- Sponsor describes statistical methods in section §10.

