5.1 Device description and intended use

Nanostim has developed a leadless cardiac pacemaker (LCP) system to eliminate leads, pockets, and connectors required by conventional pacemakers and to eliminate associated complications. This concept improves patient comfort by replacing a surgical procedure with a percutaneous one (potentially permitting implantation as an outpatient) and eliminates the scar at a conventional pacemaker's pectoral implant site.

Nanostim's LCP system consists of a pacemaker and its accessories: a programmer, introducer, delivery catheter, and retrieval catheter. The accessories are not intended for use alone or with any device other than the Nanostim pacemaker. The pacemaker and all accessories, except the programmer, are single-use devices and are supplied sterile.

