9.4.3 Post-procedure assessments

This section does not apply to subjects who were previously implanted with a Nanostim LCP.

The follow-up period is sufficient to demonstrate performance. Additionally, during this follow-up period, Sponsor will identify and assess any risks associated with adverse device effects (ADEs). Subjects will continue with follow-up visits consistent with the institution's standard of care for pacemakers. Table 1 lists the schedule of assessments.

Investigator will assess enrolled subjects, who have an LCP implant attempted but whose implant procedure cannot be completed, for AEs occurring up to 30 days post implant attempt.

Investigator will report any subjects who require LCP revision after implantation.

- If the subject has the Nanostim™ LCP removed at any time during the study, and the subject will receive another Nanostim LCP, the investigator will continue following the patient in the study.
- If the subject has the Nanostim™ LCP removed or deactivated at any time during the study, and the subject will not receive a replacement Nanostim™ LCP, the investigator will assess the subject for AEs occurring up to 30 days post revision.

Access-site management during hospital stay

Investigator will manage access sites per standard of care. Investigator will assess and document any post-procedural access-site bleeding event based on the following grading system.

ACCESS-SITE OOZING: Superficial bleeding of a cutaneous or subcutaneous origin characterized by diffuse localized bleeding and controlled with minimal care (e.g., application of manual pressure, application of sandbag).

ACCESS-SITE HEMATOMA: A localized collection of extravasated blood in subcutaneous tissue at the access site that does not require intervention. A metric ruler should be used to measure the widest portion of the hematoma.

ACCESS-SITE HEMATOMA REQUIRING INTERVENTION: A localized collection of extravasated blood in subcutaneous tissue at the access site that is considered life threatening and requires emergency wound exploration (e.g., acutely expanding hematoma, acute leg pain/numbness/swelling) and/or prolongation of hospital stay.

ACCESS-SITE RE-BLEEDING: Localized bleeding at the access site that occurs after hospital discharge. These bleeds are typically associated with an event (e.g., fall, attempted suture removal, physical activity).

Pre-Discharge Visit

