10 STATISTICAL CONSIDERATIONS

10.1 Statistical design, method and analytical procedures, sample size, level of significance and power

Refer to § 6.1 for a discussion of statistical design for the primary objective.

The sample size also permits application of the normal approximation to distributions of means. This enables the clinical study to provide confidence intervals derived from sample means and standard deviations of performance parameters (§9.1.2).

Table 2: Summary of the objectives and the analytical procedures of the clinical investigation

Objective	Type of objective	Clinical testing
180-day Complication-free rate (CFR)	Primary safety	Confidence Interval
5-year CFR	Supplementary	Confidence Interval
Implant-success rate (ISR)	Additional data	Descriptive statistics
LCP Performance ¹	Additional data	Descriptive statistics at all visits

Descriptive statistics will provide mean, standard deviation, and a two-sided 90 % confidence interval.

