16.3 Adverse device effect (ADE)

An **adverse device effect** is an adverse event related to the use of a study medical device.

This definition includes adverse events resulting from insufficient or inadequate instructions for use, deployment, implantation, installation, or operation, or any malfunction of the investigational medical device.

This definition includes any event resulting from use error or from intentional misuse of the study medical device.

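### The exclusion sentence in section 9.1.4 lacks a conjunction and can be read as leaving failed implant attempts, and any SADE in them, out of the primary 180-day complication-free rate

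*Combined protocol and SAP*

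**What the plan says.** The rule in section 9.1.4 opens: "If a subject is not successfully implanted with an LCP, signs a consent but does not undergo an implant attempt". Such subjects will be accounted for by the sponsor in the final report, "but will exclude them from the calculation of the primary endpoint (complication-free rate"). A sub-bullet follows: "A successful implant is defined as an enrolled subject leaving the implant procedure with a functioning LCP capable of pacing and sensing".

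Section 9.1.2 sets the primary endpoint as freedom from SADE at 180 days. It counts implant success rate on a different base: subjects "leaving the implant procedure with an implanted and functioning LCP device, divided by the number of subjects in whom implantation is attempted".

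For methods, 9.1.4 points to section 10, and section 10.1 points to section 6.1 "for a discussion of statistical design for the primary objective". The calculation in 6.1 is blacked out.

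On follow-up, section 9.4.3 has the investigator assess subjects "whose implant procedure cannot be completed, for AEs occurring up to 30 days post implant attempt". Section 10.2 asks for SAEs in failed attempts over the same period.

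**The concern.** Nothing in the 9.1.4 sentence says whether its two conditions must both hold or whether either is enough. If either is enough, a subject whose implant was tried and failed leaves both numerator and denominator of the primary rate.

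Such a subject can have had a SADE under the plan's own definitions. Section 16.3 says of adverse device effects: "This definition includes adverse events resulting from insufficient or inadequate instructions for use, deployment, implantation, installation, or operation". Section 5.1 says the "LCP system consists of a pacemaker and its accessories: a programmer, introducer, delivery catheter, and retrieval catheter", so harm from the introducer or delivery catheter is harm from the study device. Section 16.8 lists cardiac perforation, tamponade and venous perforation as foreseeable. A serious event of this kind that ends the procedure also makes the implant unsuccessful, and so takes itself out of the rate.

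At stake is the denominator of the primary safety rate, which section 6.1 says is to be compared with conventional pacing under a reduced non-inferiority margin. A denominator that can be read two ways can also be settled after the results are known.

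**Working it through.** **The plan's own figure.** The 300 subjects for the 180-day rate (section 9.3.4) cannot be reproduced, because the reference rate, margin, alpha, power and dropout allowance are not visible. The point does not depend on that number.

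**The two readings**

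- *Both conditions required.* Only subjects with no attempt are excluded. The phrase about unsuccessful implantation is then redundant, since a subject with no attempt cannot have been implanted. The sub-bullet has no work to do either; implant success rate does not need it, because 9.1.2 has its own definition.
- *Either condition enough.* Failed attempts and subjects with no attempt are both excluded. Each phrase has a function, and the sub-bullet draws the line between failed and successful attempts.

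The second is the more natural reading. It is not the only one.

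**Bias on the second reading.** Let f be the share of attempts that fail, and p_fail and p_succ the SADE risks in failed and successful attempts.

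- Rate reported: 1 - p_succ
- Rate over all attempts: 1 - [(1 - f) p_succ + f p_fail]
- Difference (reported minus all attempts): f x (p_fail - p_succ)

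The documents give none of the three inputs. Assuming p_succ = 6%, f = 1 to 10% and p_fail = 0 to 50%, the difference in percentage points is:

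| f | p_fail 0 | 6% | 10% | 25% | 50% |
|---|---|---|---|---|---|
| 1% | -0.06 | 0 | +0.04 | +0.19 | +0.44 |
| 5% | -0.30 | 0 | +0.20 | +0.95 | +2.20 |
| 10% | -0.60 | 0 | +0.40 | +1.90 | +4.40 |

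**In counts.** Assume 300 attempts, m failures and s failures with a SADE. (Whether the 300 PMCF subjects include failed attempts is not visible.) The difference is (s - 0.06m)/300. Each omitted SADE adds 1/300 = 0.33 points; each omitted failure subtracts 0.06/300 = 0.02 points. The sign turns upward once s exceeds 0.06m: 0.18 for m = 3, 0.9 for m = 15, 1.8 for m = 30. That means 1, 1 and 2 SADEs.

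Example with m = 15 and 17 SADEs in 285 successful implants, reported rate 1 - 17/285 = 94.04%:

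- s = 0: all attempts 1 - 17/300 = 94.33%, difference -0.30
- s = 1: 1 - 18/300 = 94.00%, +0.04
- s = 2: 1 - 19/300 = 93.67%, +0.37
- s = 3: 1 - 20/300 = 93.33%, +0.70

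**Scale.** At 94% and n = 300, a two-sided 90% half-width is 1.645 x sqrt(0.94 x 0.06/300) = 2.26 points. Of the 15 cells in the table, only the last exceeds it. Section 10.1 gives the 90% level for descriptive statistics; the level for the primary rate is not visible.

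**Effect of the shorter follow-up.** For s = 2, censor the 13 event-free failures at day 30 and assume 12 of the 17 other SADEs fall by then. Kaplan-Meier gives (1 - 14/300) x (1 - 5/273) = 93.59%, against 93.67% crude. Counting failed attempts is therefore workable with the data already collected.

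**The case against.** *Section 6.1 may define the analysis set.* This stands as a limit: the point rests on the visible text.

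*Redundancy is weak evidence in a loosely drafted document.* Successful implantation is defined twice on any reading. Section 10.2 also treats the two groups separately: the investigator supplies data on failed attempts, and only subjects with no attempt are said to be reported by the sponsor, which echoes the sponsor's accounting in 9.1.4. This gives the narrow reading some support and makes the choice closer, but does not decide it.

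*Many failures may be event-free.* The reasons listed in 10.2 are anatomical or access problems. If failures carry fewer SADEs than successes, the exclusion makes the rate slightly worse. This stands.

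*Some subjects enter already implanted* (synopsis and section 9.3.4). They bring no failed attempts and lower f. This stands, and the repair must provide for them.

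*A rate among successful implants can be a legitimate target*, and the comparator in 6.1 may be counted that way. This stands as a reason to keep that rate, not to leave the sentence unclear.

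A reader might infer more than the documents support:

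- *That the plan definitely drops these SADEs and so inflates its safety rate.* Neither the reading nor the sign is established.
- *That the short follow-up proves exclusion.* Section 9.4.3 sets the same 30-day limit for implanted subjects whose device is removed or deactivated and not replaced.
- *That the events are lost.* They are collected to 30 days, adjudicated by the Clinical Event Committee if device or procedure related (section 16), open to periodic board review (section 17) and reported with the PMCF safety data (section 6.3). None of this puts them back into the primary rate, but the safety evidence is not suppressed.

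**Conclusion.** The point holds as a defect of wording in the rule that sets the primary denominator. On the more natural reading, inclusion depends on how the procedure ended, an outcome linked to the endpoint, and no visible section restores a SADE from a failed attempt to the rate. SADEs in subjects who leave with a functioning device are counted on either reading. Section 9.1.4 names only the primary endpoint, so the point is confined to it.

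Sign and size are unknown. The bias is upward only if SADEs are more frequent in failed than in successful attempts, and zero if the risks are equal. Over the assumed ranges it runs from -0.6 to +4.4 points, with both ends corner cases, and is mostly smaller than the sampling half-width of about 2.3 points. Its effect on the non-inferiority conclusion cannot be judged, because the margin and reference rate are not visible. The case for change is an unambiguous analysis set, not a demonstrated distortion.

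**What to change.** 1. Reword 9.1.4 so that only subjects with no implant attempt are excluded.
2. For subjects whose implant is attempted within this study, count every attempt in the primary rate, with a SADE during the attempt or the next 30 days as an event. State how event-free failed attempts contribute, for example censored at last contact in a Kaplan-Meier estimate.
3. Make 6.1 and 9.1.4 state the same set.
4. Report the successful-implant-only rate as a sensitivity analysis, and use it for the matched comparison if the comparator in 6.1 counts only completed implants.
5. Identify subjects enrolled already implanted separately. They cannot contribute failed attempts and are selected for success.

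No new data are needed, since events in failed attempts are already recorded to 30 days. The cost is a protocol amendment and a little more analysis. Under section 12, a change affecting scientific soundness needs written ethics committee approval, and competent authority approval where applicable, at up to 100 sites. The reported rate may also be less favourable.

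Section 10.2 times the follow-up of subjects with no attempt from an attempt that never took place. That is a separate editorial correction.
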